8.9.2 Sample Collection

The following samples will be stored in the RBR and used for research purposes, including, but not limited to, research on biomarkers related to study treatment, diseases or drug safety:

- C1D1 RBR samples.
- Leftover plasma samples.
- Leftover serum samples.
- Leftover blood samples.
- Leftover tissue (fresh tumor, fresh skin, archival tumor) samples.
- Leftover blood samples for DNA extraction.

Optional Stool Samples

Participants will be given the option of consenting to provide stool samples. Dietary intake is a central determinant of changes in the microbiota, which influences the immunological responses in the intestine and thereby affects potential AEs during immunotherapies. A nutritional assessment will therefore be performed at baseline to better correlate the profiles of the microbiota to safety-relevant immune responses.

Upon consent, participants will be requested to provide optional stool samples at the following time points:

- At screening, any time prior to C1D1.
- On-treatment, every 12 weeks (± 14 days).
- Upon occurrence of colitis, as assessed and confirmed by the Investigator.

Screening stool samples of participants who are not enrolled in the study will be destroyed.

Additional stool samples may be requested at any time point per Investigator's discretion, for example when resuming treatment post colitis.

For sampling procedures, storage conditions, and shipment instructions, see the sample flowchart and additional instruction documents.

8.9.3 Leftover of Sample Derivatives such as DNA and RNA

The samples collected for DNA extraction include, but is not limited to genomic analysis and may be sent to one or more laboratories for analysis of germline or somatic mutations via WGS, WES, NGS, or other genomic analysis methods.

Genomics is increasingly informing researcher's understanding of disease pathobiology. WGS provides a comprehensive characterization of the genome and, along with clinical data collected in this study, may increase the opportunity for developing new therapeutic approaches. Data will be analyzed in the context of this study but may also be explored in aggregate with data from other studies. The availability of a larger dataset will assist in identification of important pathways, guiding the development of new targeted agents.

Samples may be sent to one or more laboratories for analysis for of germline or somatic mutations via WGS/WES, or other genomic analysis methods. Genomics is increasingly informing researchers' understanding of disease pathobiology. WGS and WES provide a comprehensive characterization of the genome and exome, respectively, and, along with clinical data collected in this study, may increase the opportunity for developing new therapeutic approaches or new methods for monitoring efficacy and safety or predicting which patients are more likely to respond to a drug or develop AEs.

Participants will not be identified by name or any other personally identifying information. Data generated from RBR samples will be analyzed in the context of this study but may also be explored in aggregate with data from other studies. The availability of a larger dataset will assist in identification and characterization of important biomarkers and pathways to support future drug development.

For all samples, dates of consent and sample collection should be recorded on the associated RBR page of the eCRF. Details on processes for collection and shipment of these samples can be found in separate sample documentation.

RBR samples will be stored and used until no longer needed or until they are depleted. The RBR storage period will be in accordance with the IRB/EC-approved ICF and applicable laws (e.g., Health Authority requirements).

The repository samples will be subject to the confidentiality standards (as described under Confidentiality and in [Appendix 1](#)).

8.10 HEALTH ECONOMICS OR MEDICAL RESOURCE UTILIZATION AND HEALTH ECONOMICS

Health Economics/Medical Resource Utilization and Health Economics parameters are not evaluated in this study.

8.11 TIMING OF STUDY ASSESSMENTS

8.11.1 Screening and Pre-treatment Assessments

Written informed consent for participation in the study must be obtained before performing any study-specific screening tests or evaluations. Pre-screening ICFs and ICFs for enrolled participant and for participants who are not subsequently enrolled will be maintained at the study site.

All screening and pre-treatment assessments (related to entry criteria), must be completed and reviewed to confirm that participants meet all eligibility criteria. The Investigator will maintain a screening log to record details of all participants screened and to confirm eligibility or record reasons for screening failure.

An Eligibility Screening Form documenting the Investigator's assessment of each screened participant with regard to the protocol's inclusion and exclusion criteria is to be completed by the Investigator and kept at the investigational site.

8.11.2 Assessments during Treatment

Under no circumstance will participants who enroll in this study and have completed treatment as specified, be permitted to re-enroll in the study.

All assessments must be performed as per SoAs (Section 1.3). Assessments scheduled on the day of study treatment administration should be performed prior to administration of study treatment, unless otherwise noted in the SoAs.

8.11.3 Assessments at Study Completion/Early Termination Visit

End of Treatment/Early Discontinuation: Participants who complete the treatment or discontinue from the study early, will be asked to return to the clinic 28 (\pm 7) days after the last dose of study drug or last data point. The visit at which a response assessment shows progressive disease may be used as the Early Discontinuation visit. Assessments should be completed as detailed in the SoA (Section 1.3).

8.11.4 Follow-Up Assessments

Safety Follow-Up/End of Study: Participants who complete the treatment or discontinue from the study early, will be asked to return to the clinic 135 (\pm 30) days after the last dose of study drug or last data point determined for an End of Treatment Visit. Assessments should be completed as detailed in the SoA (Section 1.3).

Survival Follow-Up: The sites will provide to the Sponsor (using a designated section of the eCRF) with an update on survival status 90 (\pm 7) days after the Safety Follow-Up visit and then every 3 months (\pm 2 weeks) thereafter up until 24 months post initial treatment (or until study closure) for each participant enrolled in the study. Patients who screen-failed due to the ROPRO score will also be followed up for survival.

After the study completion/early termination visit, AEs should be followed as outlined in Sections 8.3.1 and 8.3.3.

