1.3 SCHEDULE OF ACTIVITIES

The schedule of the activities (SoA) for Parts I, II, and III is provided in [Table 1](#). The SoA for PK/PD sampling is provided in [Table 2](#) for Part I and in [Table 3](#) for Parts II and III.

Table 1 Schedule of Activities for all Parts (21-Day Cycle, Q3W)

Protocol section	Cycle	Pre-screening	Screening / Baseline	Cycle 1				Cycle 2				Cycle 3				Cycle 4				Cycle 5	Subsequent Cycles to 24 Months	End of Treatment (EoT) / Early Discontinuation	End of Study / Safety Follow-up	Survival Follow up	Unscheduled Safety (for IRR/CRS refer to Table 2 and Table 3)	
	Study visit window			± 1 d	± 2d	± 2d		± 2d	± 2d	± 2d	± 2d	± 2d	± 1 d	± 2d	± 2d	± 2d	± 2d	28 (± 7) days after last dose	135 (± 30) days after last dose	90 (± 7) days after Safety FU visit and then every 3 months (± 14 days)						
	Day		D-28 to D-1	Day 1	Day 2	Day 4	Day 8	Day 15	Day 1	Day 2	Day 8	Day 1	Day 2	Day 8	Day 15	Day 1	Day 2	Day 4	Day 8	Day 15	Day 1	Day 1				
ASSESSMENTS																										
8.8.1	Pre-Screening ICF for archival tumor	x (Part II only)																								
8.2.11	Electronic symptom questionnaire (optional)	x (Part II only)																								
5.1	Informed Consent	x																								
8.2.8	Eligibility criteria	x																								
8.2.8	Demography	x																								
8.2.1	Medical/Cancer History	x																								
8.1.1	Complete physical exam	x																								
8.2.6	Brain CT/MRI	x																								(x)
8.2.6	Chest X-ray	x																								(x)
8.2.5	Echocardiography (TTE/MUGA)	x																								
8.2.3	Oxygen saturation	x																								
8.2.8	Smoking status	x																								
8.2.10	ROPRO	x																								
8.2.2	Height	x																								
8.2.9	Weight	x x																			x x x x					(x)
8.2.9	ECOG	x x																			x x x x					(x)
8.2.3 and 6.1.1	Vital Signs	x	Section 6.1.1	x	x	x	x	Section 6.1.1	x	x	Section 6.1.1	x	x	x	Section 6.1.1	x	x	x	x	Section 6.1.1	Section 6.1.1	x	x			(x)
8.2.1	Targeted physical exam			x x x x x	x x x x x	x x x x x	x x x x x		x x x x x	x x x x x		x x x x x	x x x x x	x x x x x		x x x x x	x x x x x	x x x x x	x x x x x							(x)
8.2.4	Triplicate 12-lead ECG	x	pre-dose					pre-dose			pre-dose															(x)
8.3	Adverse Events																									(x)
6.5	Previous and Concomitant Treatments																									(x)
STUDY DRUG ADMINISTRATION																										

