3. OBJECTIVES AND ENDPOINTS

The objectives and corresponding endpoints are provided in [Table 4](#).

Note: Due to the adaptive nature of Part III, additional cohorts, which are not described in this protocol, may be added in the study (see [Appendix 6](#), [Appendix 7](#), [Appendix 8](#), and [Appendix 9](#)). For a rationale, see [Appendix 9](#).

Table 4 Objectives and Endpoints

Objectives	Endpoints
Primary	
All Parts (Dose Escalation [Part I] and Dose Expansion [Part II and Part III])	
To evaluate the safety, tolerability, maximum tolerated dose (MTD) and/or recommended Phase 2 dose (RP2D) (Part I only) of RO7296682 when administered in combination with atezolizumab.	
 • Nature and frequency of adverse events (AEs) with severity determined according to NCI CTCAE v5.0 • Nature and frequency of dose-limiting toxicities (DLTs) in Part I
Primary (Dose Expansion Part II and Part III)	
To evaluate the preliminary anti-tumor activity of RO7296682 when administered in combination with atezolizumab.	
 • Objective response rate (ORR) according to RECIST v1.1
Secondary (Dose Escalation, Part I)	
To evaluate the preliminary anti-tumor activity of RO7296682 when administered in combination with atezolizumab.	
 • ORR according to RECIST v1.1
Secondary (Dose-Escalation [Part I] and Dose Expansion [Part II and Part III])	
To further characterize the anti-tumor activity of RO7296682 when administered in combination with atezolizumab.	
 • Disease control rate (DCR) defined as response rate (RR) and stable disease (SD) • Duration of response (DoR) • Progression-free survival (PFS) 
All according to RECIST v1.1
 
 • Overall survival (OS), if data are mature at the time of analysis
To investigate the pharmacokinetic (PK) profile of RO7296682 and atezolizumab after administration of RO7296682 in combination with atezolizumab.	
 • PK profiles and parameters derived for RO7296682 and atezolizumab, as appropriate, including but not limited to: 
 ○ Area under the curve (AUC) ○ Minimum (C_{\min}) and maximum (C_{\max}) concentration ○ Time of maximum concentration (T_{\max}) ○ Volume of distribution at steady-state (V_{ss}) ○ Half-life ($t_{1/2}$)

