4.1.1 Length of the Study

The maximum duration of the study for each participant will be up to 31 months, divided as follows:

- Screening: Days -28 to -1.

- Treatment Period: C1D1 to Month 24 (may be modified if supported by emerging data).
- End of Treatment Visit: 28 (\pm 7) days after last dose
- Safety follow-up: 135 (\pm 30) days after last treatment with RO7296682 in combination with atezolizumab.
- Survival follow-up: 90 (\pm 7) days after the safety follow-up visit; then every 3 months (\pm 14 days) until death, lost to follow-up, or until study closure by the Sponsor, whichever occurs first.

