DoR will be calculated for participants who have a best overall response of CR or PR and defined as the time from first occurrence of a documented OR until the time of

documented disease progression or death (death within 30 days from last study treatment) from any cause, whichever occurs first. Censoring methods will be the same as the one applied for progression-free survival (PFS; on-treatment).

PFS on treatment will be defined as the time from study treatment initiation (C1D1) to the first occurrence of documented disease progression (based on RECIST v1.1 Investigator's assessment) or death from any cause, whichever occurs first. For participants who do not have documented progressive disease or death (within 30 days from last study treatment) during the study, PFS will be censored at the day of the last tumor assessment. Participants without any post baseline assessments or with all post-baseline assessments having unknown result/response but known to be alive at the clinical cut off for the analysis will be censored at the date of study treatment initiation plus one day.

Sensitivity analyses of response endpoints (ORR, DCR, DoR, and PFS) may include the evaluation of response according to iRECIST and the evaluation of response from an independent centralized review.

OS is defined as the time from the first dose of study treatment to the time of death from any cause. Participants who are still alive at the time of analysis will be censored at the time of their last study assessment (for active participants) or at the last date known alive (for participants in follow-up).

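### Section 8.11.4 stops survival follow-up 24 months after first treatment, while the synopsis, Section 4.1.1 and Table 1 do not, so the end of OS follow-up depends on time on treatment

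*Combined protocol and SAP*

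**What the plan says.** The protocol gives two different ends for survival follow-up.

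- **Synopsis and Section 4.1.1:** contacts continue "until death, lost to follow-up, or until study closure by the Sponsor, whichever occurs first".
- **Table 1 (Section 1.3):** contacts are scheduled at "90 (± 7) days after Safety FU visit and then every 3 months (± 14 days"), with no end date.
- **Section 8.11.4:** the quarterly updates run "thereafter up until 24 months post initial treatment (or until study closure) for each participant enrolled in the study".

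Four other provisions bear on the point.

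- The treatment period is "C1D1 to Month 24 (may be modified if supported by emerging data").
- The safety follow-up visit is "135 (± 30) days after last dose".
- Section 9.4.2 states that "OS is defined as the time from the first dose of study treatment to the time of death from any cause". Living participants are censored at their last study assessment if active, "or at the last date known alive (for participants in follow-up").
- Section 3 lists as a secondary endpoint "Overall survival (OS), if data are mature at the time of analysis".

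The synopsis and Section 4.1.1 also state a maximum of 31 months per participant and list survival follow-up among its components.

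**The concern.** A site that follows Section 8.11.4 stops contacting people whom Section 4.1.1 tells it to keep following. The cap counts from first treatment, but the contacts it limits count from the last dose. How much survival follow-up a participant receives therefore depends on how long that participant was treated.

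The contact schedule matters to the analysis because a living participant in follow-up is censored at the last date known alive. Section 7.2 has participants treated until progression, unacceptable toxicity or withdrawal of consent, so long-treated participants are mainly those who have not progressed. If only they remain under observation late in the curve, censoring is tied to a prognostic variable measured after baseline. The tail of the OS curve would then be expected to look too favourable.

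**Working it through.** **Inputs.** Maximum treatment 24 months (4.1.1); safety visit at last dose + 135 days, window ± 30 (Table 1); first survival contact 90 days after that, window ± 7 (Table 1); repeats every 3 months; cap at 24 months from first treatment (8.11.4). One month = 365.25/12 = 30.44 days, so 24 months = 730.5 days.

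**1. The plan's own 31-month maximum.** Screening + treatment + latest safety visit = 28 days + 24 months + 165 days = 24 + 193/30.44 = 30.3 months, roughly the stated 31. Screening + treatment + first survival contact at nominal timing = 24 + (28 + 225)/30.44 = 32.3 months. The stated maximum is met only if survival follow-up is left out, although Section 4.1.1 lists it as included.

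**2. First survival contact.** Last dose + 135 + 90 = last dose + 225 days = 7.4 months. After 24 months of treatment it falls at 24 + 7.4 = month 31.4 from first treatment.

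**3. Last dose beyond which the first contact passes the cap.** 730.5 − 225 = 505.5 days = month 16.6.
- Earliest windows: 105 + 83 = 188 days; 730.5 − 188 = 542.5 days = month 17.8.
- Latest windows: 165 + 97 = 262 days; 730.5 − 262 = 468.5 days = month 15.4.

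**4. Last dose beyond which the safety visit itself passes month 24.** 135/30.44 = 4.4 months; 24 − 4.4 = month 19.6.

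**5. Last scheduled contact under the cap, at nominal timing.** The strict reading applies the cap to the first 90-day contact. The lenient reading applies it only to the quarterly repeats. All times are months from first treatment.

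| Last dose | Safety visit | Last contact, strict | Last contact, lenient |
|---|---|---|---|
| 6 | 10.4 | 22.4 | 22.4 |
| 12 | 16.4 | 22.4 | 22.4 |
| 16.6 | 21.0 | 24.0 | 24.0 |
| 16.7 | 21.1 | 21.1 | 24.1 |
| 18 | 22.4 | 22.4 | 25.4 |
| 20 | 24.4 | 24.4 | 27.4 |
| 22 | 26.4 | 26.4 | 29.4 |
| 24 | 28.4 | 28.4 | 31.4 |

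For last doses up to month 16.6, the last scheduled contact falls between months 21.0 and 24.0 on either reading. Later last doses give months 21.1 to 28.4 on the strict reading and 24.0 to 31.4 on the lenient one. Scheduled observation after month 24 is therefore confined to those treated beyond about month 19.6 (strict) or month 16.6 (lenient).

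**6. Without the cap.** Every survivor has a first contact at last dose + 225 days and quarterly contacts afterwards, so the end of scheduled follow-up no longer depends on time on treatment.

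**The case against.** Much of the case on the other side narrows the point, and that part stands.

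- **The cap may not reach the first contact.** The sentence can be read as limiting only the quarterly repeats. Long-treated participants then get one contact. A reader might infer that they certainly get none; the text does not establish that.
- **The study-closure alternative is ambiguous.** If the parenthesis means whichever date is later, the cap may not bind. The sentence does not say so, and the ambiguity needs fixing in any case.
- **The longest-treated are not observed for less time than others.** A reader might infer that the longest responders lose the most survival data. On the strict reading they are seen at the safety visit up to month 28.4, later than early stoppers. Among those treated beyond month 16.6, only the group stopping at about 16.6 to 19.6 months ends short of month 24, by up to about 3 months. Compared with the uncapped text everyone loses later contacts, and early stoppers lose more.
- **The consequence is limited.** OS is secondary, tabulated only if mature, and Section 9.1 plans no hypothesis test. Section 9.5 names OS among the endpoints that could overrule the non-binding Part III futility rules, but the late tail is unlikely to be available by then.
- **Deaths are reportable anyway.** Appendix 2, Section 5.1 asks for all deaths after the adverse event period. It sets no contact schedule, however, so it does not establish who is still alive.

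None of this removes the contradiction or the dependence on time on treatment. If the cap binds, that dependence holds on both readings of what it covers.

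**Conclusion.** The protocol is wrong as written: Section 8.11.4 contradicts the synopsis, Section 4.1.1 and Table 1. Followed literally, its cap makes the last scheduled vital-status contact depend on treatment duration. The first survival contact falls beyond the cap for a last dose after about month 16.6 (15.4 to 17.8 across the windows). After month 24 the OS risk set consists only of long-treated participants, so the late Kaplan-Meier tail is subject to informative censoring, probably in the favourable direction.

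The size is modest. The distortion lies in the tail, and the curve before about month 21 is little affected. A reader might infer that OS as a whole is biased; the documents do not support that. No primary endpoint or formal test is touched. The number of participants affected cannot be given, because the protocol states no expected distribution of time on treatment.

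The conclusion assumes that the cap binds, that contacts occur at nominal times, and that treatment duration is prognostic. The correction should be made, but the point does not put the main objectives in doubt.

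**What to change.** Remove the 24-month limit from Section 8.11.4 and give it the same end rule as the synopsis and Section 4.1.1, with Table 1 unchanged. In the same edit, reword the 31-month maximum in the synopsis and Section 4.1.1 so that it covers screening, treatment and safety follow-up and excludes survival follow-up. Deleting the cap alone would leave open-ended follow-up inside a fixed maximum.

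The documents do not show which version the sponsor intended. If a cap is wanted, truncate OS at 24 months for every participant and collect vital status at month 24 for all, including those still on treatment or in safety follow-up. Say also whether study closure shortens or extends the period.

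The cost of the preferred change is a few sentences plus quarterly status checks that Section 4.1.1 already requires. It helps only while participants can still be contacted.

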8.11.5 Assessments at Unscheduled Visits

For activities that required to be performed in case of an unscheduled visit, refer to the SoA (Section 1.3).

9. STATISTICAL CONSIDERATIONS

9.1 STATISTICAL HYPOTHESES

There is no formal statistical model or pre-planned formal hypothesis testing in this study.

9.2 SAMPLE SIZE DETERMINATION

Part I:

The maximum total number of participants in the dose escalation portions of Part I will be approximately 60 DLT-evaluable participants on a Q3W schedule. The exact sample size cannot be pre-determined and depends on the number of cohorts needed to reach

a MTD and/or RP2D. However, the simulations presented in Section 3 of [Appendix 11](#) show simulated sample sizes in a variety of toxicity scenarios.

Part II:

Approximately 60 CPI-experienced participants with NSCLC, HNSCC, and MEL will be enrolled in Part II in order to have around 10 participants per indication and aim for at least 30 response-evaluable participants with an ██████████, which is confirmed in the fresh baseline biopsy. With around 10 participants per indication, there will be sufficient number for decision making to open Part III cohorts ([Table 18](#)). Participants with MEL, NSCLC and HNSCC which are not amenable to standard treatment, will be enrolled in Part II; however, if emerging data suggest alternative indications should be pursued, then participants with ovarian, esophageal, TNBC or other indications as deemed fit may be considered.

Part III

In Part III, each tumor-specific cohort for NSCLC, HNSCC, and MEL may be opened for approximately 20 response-evaluable participants given that any of the gating criteria defined in [Section 9.5](#) are met based on the corresponding indication in single agent dose expansion of WP41188, Part I of this study, or Part II of this study. The futility interim analysis will be performed when the first 10 response-evaluable participants have mature data in each tumor-specific cohort. The detail of the futility analysis is provided in [Section 9.5](#).

For the CPI-experienced HNSCC cohort in Part III, the sample size of 20 response-evaluable participants allows to declare futility with a probability of 92% under the assumption that the true ORR is 5%, based on the posterior probability for ORR to be below 20% with a 70% confidence level.

For CPI-experienced NSCLC cohort in Part III, the sample size of 20 response-evaluable participants allows to declare futility with a probability of 87% chances under the assumption that the true ORR is 10%, based on the posterior probability for ORR to be below 25% with a 70% confidence level.

For CPI-experienced MEL cohort in Part III, the sample size of 20 response-evaluable participants allows to declare futility with a probability of 83% under the assumption that the true ORR is 15%, based on the posterior probability for ORR to be below 30% with a 70% confidence level.

